1.1. State of the art, knowledge needs and project objectives

Sleep has been underrated for decades in medicine [1] despite the fact that improved sleep reduces psychiatric symptoms [2] and poor sleep is longitudinally linked to impaired somatic health [3]. In 2017, the Nobel Prize for Medicine or Physiology was awarded to scientists who showed that humans have a network comprising of timekeeping genes that are repeated in a daily cycle. These timekeeping genes are associated with timing of sleep and wakefulness as well as mental disorders such as depression, bipolar disorders, and other mood disorders. This important acknowledgment of sleep and circadian rhythms' relation to mental health, has turned the wheel towards increased focus on sleep-related scientific knowledge [1]. The main idea behind this project is to bring a focus on sleep into psychiatric care (SIP) and to provide an evidence-based approach of delivering non-pharmacological sleep-treatment to people with psychiatric illness.

The projects in this proposal are based on several important theoretical findings. First, disrupted and poor sleep are associated with the development, relapse, or worsening of mental disorders and also increased suicidal ideation [4]. Polysomnography studies on sleep and mental disorders show that problems with maintenance of sleep are observed in most mental disorders while sleep architecture alterations compared to normal sleep are observed in all mental disorders except for ADHD and seasonal affective disorder [5]. Sleep and mental health have a bidirectional relationship, but there is a knowledge gap on whether interventions to improve sleep also improve mental health in patients with moderate to severe psychiatric illness [2]. About 50% of patients visiting their general practitioner fulfil the criteria for chronic insomnia [6] and 45-70% of patients with depression, bipolar disorder, anxiety disorder, and PTSD have been shown to have significant sleep disruption [7, 8]. Cognitive behavioural therapy for insomnia (CBTi) is the recommended treatment option for chronic insomnia disorder worldwide, but its effect on patients with comorbid moderate to severe psychiatric illness is mainly documented in single-disorder randomized controlled studies (RCTs) [6]. A recent feasibility study from Sweden showed that CBTi delivered in groups is a clinically feasible treatment option for insomnia in an outpatient setting among patients diagnosed with depression, bipolar disorder, anxiety disorders, and PTSD [7]. In a recent series on sleep and sleep disorders in the Lancet, the authors point out that very few high-quality intervention studies exist and that treatment for circadian rhythm disorders are hindered by a scarcity of tools for measuring sleep and circadian physiology [9]. Chronotherapy (e.g., sleep hygiene, timed light exposure, and the use of chronobiotic medications), shows promising effects within psychiatric treatment [9]. Also, a high prevalence of personality disorders has been found decades ago in circadian rhythm sleep disorders, though the focus on this comorbidity seem to have gotten increased attention in later years [10]. Transdiagnostic interventions, which are based on the assumption that many differential disorders share common etiological and maintenance process [11], targeting sleep in psychiatric illness has received increased attention in the past decade [9, 12-14]. Also, disturbances of the circadian system have been

implicated in the development of several somatic illnesses such as cancer and cardiovascular diseases as well as in neuropsychiatric disorders [9]. Hence, sleep plays a pivotal role for health in the entire organism.

In this project the objective is to investigate the effects of two non-pharmacological group-based treatments for patients with insomnia and the most common circadian rhythm sleep-wake disorder; delayed sleep-wake phase disorder (DSWPD), respectively, in which both sleep disorders are comorbid with moderate to severe mental illness. We will investigate the effect on subjective and objective sleep measures and on symptoms of psychiatric illness. By treating the sleep disorders adjacent to their mental illness, we will be able to fill the gaps of the abovementioned knowledge needs. We will examine the potential benefits of sleep-treatment on a wide array of symptoms and areas of human functioning, because sleep plays a role in all aspects of the human body.

1.2. Novelty and ambition

The current project is highly innovative and underlines the importance of cross-disciplinary - including user-representative - collaboration. Findings from this study will improve our understanding of the development, relapse, and remission of moderate to severe mental disorders, the importance of sleep and the sleep-wake cycle including neurophysiology in health and illness and could change the way we design future package sequences in the mental health care sector. This could lead to new scientific discoveries and improved treatment interventions. The results have the potential to change the way we think about, teach new therapists (medical doctors, psychologists, psychiatric nurses, and other health personnel), and not the least the way we treat patients with mental illness and comorbid sleep disorders. This project is to our knowledge the first to combine state-of-the-art knowledge about chronotherapy with knowledge from the extensive research on the benefits of CBTi on sleep and psychiatric symptoms. It is also the first to examine the potential benefits of non-pharmacological sleep treatment in moderate to severely mentally ill patients on a wide array of functionalities.

Particularly innovative aspects of this project:

- We focus our attention on a patient group otherwise often excluded from research protocols, even though a vast amount of time and money is invested every day to treat this patient group.
- We treat sleep disorders co-jointly with psychiatric disorders in a psychiatric setting.
- The broad outcome measures and the combination of self-report and objective measures.
- We will study a treatment already implemented as a treatment in a clinic, making it easier and more feasible to implement in other clinics. The project is hence based on clinical practice that already is experienced as effective and appreciated by therapists and patients. We now plan to test this clinically successful model with gold-standard evidence-based methodology.
- The sleep-treatment in groups is a cost-effective way of delivering sleep-treatment and we do it in a slow open fashion where patients can be referred anytime. After the pre-consultation with a member of the sleep-team, a date of sleep-treatment initiation is given, regardless of waitlists. This is a flexible format and does not require a lot of resources in the clinic.
- We will study the psychophysiology (such as blood pressure and heart-rate-variability; HRV) in patients with sleep- and psychiatric disorder. This may lead to new insights into the interconnection between sleep-wake regulation, psychophysiology, and psychiatric symptoms.
- We will investigate whether personality traits become changed in 12 months in patients with sleep disorders and psychiatric illness after successful treatment, which has not been investigated before, only suggested by several researchers in the field.
- We evaluate personality disorders (using a diagnostic manual, the SCID-5-PF) in all patients with DSWPD, which has been documented in the 1990's to be prevalent in circadian rhythm sleep disorders. This has not been taken further scientifically for two-three decades. The knowledge we

will gain from this, will not only be important in the field of sleep and circadian rhythm sleep disorders, but also in the field of personality disorders.

- We will study work attendance, welfare benefits, medication use, suicide attempts and admittances in psychiatric care before, during and after the non-pharmacological sleep-treatment.
- We are conducting two RCTs in a more naturalistic setting than what is often the case since the intervention group and control group are in outpatient psychiatric treatment during the experimental period. This improves the generalizability to clinical settings, which often is a limitation in RCTs.
- We build on the new and innovative research that indicates dark-therapy (in our project by using blue light blocking glasses (bb-glasses) as a promising treatment for mental illness and sleep disorders, for the first time investigating this as an additive treatment to more established treatment protocols in a group of patients with identified sleep disorders comorbid to moderate to severe mental illness. This along with non-pharmacological, psychological and behavioral treatment, represents a much desired alternative to the use of hypnotics to mend sleep problems.

Although the treatment basis in this project is not new, this is the first study to use the research in treatment for insomnia and DSWPD without excluding moderate to severe mental illness. It is also the first RCT to our knowledge to study the effect of treatment for insomnia and DSWPD on such a wide array of functionalities as planned here, in a group setting, in a naturalistic context. We use state-of-the-art treatment and implement it in an outpatient psychiatric clinic. The treatment has so far mainly shown effect for patients with sleep disorders only or just mild to moderate specific mental illnesses such as depression, bipolar disorder, or ADHD. Our ambition is to investigate - and if the results do not contradict our hypotheses - later develop a model and manual for non-pharmacological sleep treatment in groups for people with psychiatric illness into a recommended standard, first-choice treatment for comorbid sleep disorders in moderate to severe mental illness. We plan to develop treatment manuals which ease the transferability to other psychiatric settings. The model is designed to fit the government-regulated package sequences all patients in psychiatric care are required to receive. We argue that the project also has an innovative side where established treatment is being used in a new manner, in a new setting and where it is possible to test the treatment digitally (or hybrid with face-to-face and digital follow-up) in later studies.

1.3. Research questions and hypotheses, theoretical approach and methodology

We will test the following hypotheses in two work-packages (WPs):

1. An RCT with 60 psychiatric outpatients with comorbid insomnia and moderate to severe mental illness to investigate the positive impacts of an additive group-based treatment for insomnia compared to treatment as usual in psychiatric care while on a wait-list for non-pharmacological sleep-treatment in groups.
2. An RCT with 60 outpatients with comorbid DSWPD and moderate to severe mental illness to investigate the positive impacts of an additive group-based treatment for DSWPD compared to treatment as usual in psychiatric care while on a wait-list for non-pharmacological sleep-treatment in groups.

The specific aims of this project are to test the following hypotheses:

WP 1

Primary hypothesis: Group-based sleep intervention based on CBTi reduces insomnia symptoms and symptoms of anxiety and depression significantly more than treatment as usual while on a waitlist for non-pharmacological sleep-treatment in groups (TAU + WL).

Primary outcome measures: Insomnia Severity Index (ISI), the Bergen Insomnia Scale (BIS), and Sleep Onset latency (SOL), Wake after sleep onset (WASO), and Sleep efficiency (SE) from sleep diaries, Becks Depression Inventory (BDI-II) and Becks Anxiety Inventory (BAI).

Secondary hypothesis: Group-based sleep intervention based on CBTi reduces symptoms in a range of areas including fatigue, sleep, attention deficits, dysfunctional beliefs about sleep, and improves well-being, attention, and daytime function significantly more than treatment as usual while on a waitlist for non-pharmacological sleep-treatment in groups (TAU + WL).

The use of bb-glasses enhances the effect of the group-based treatment for insomnia on SOL.

WP 2

[figure not shown]
Primary hypothesis: Group-based sleep intervention with light therapy at gradually advanced timing advances sleep timing and reduces symptoms of anxiety and depression significantly more than treatment as usual while on a waitlist for non-pharmacological sleep-treatment in groups (TAU + WL).

Primary outcome measures: Measured subjectively and objectively by sleep diaries, Genactiv actigraphy, and saliva samples (intraindividual variation of rise time (IIV), dim light melatonin onset (DLMO), rise /wake up-time), Becks Depression Inventory (BDI-II) and Becks Anxiety Inventory (BAI).

Secondary hypothesis: Group-based sleep intervention with light therapy at gradually advanced timing reduce symptoms in a range of areas including fatigue, sleep, attention deficits, dysfunctional beliefs about sleep and improve well-being, attention, and daytime function significantly more than treatment as usual while on a waitlist for non-pharmacological sleep-treatment in groups (TAU + WL).

The use of bb-glasses enhances the effect of the group-based treatment for DSWPD on SOL.

Figure 1. Overview of the project and the two WPs.

WL= Wait list. TAU=treatment as usual, bb-glasses=Blue-blocking glasses

Two randomized controlled trials (RCTs) will be undertaken in order to obtain an evidence-based treatment model in psychiatric outpatient care for patients with moderate to severe mental illness and comorbid sleep disorders (insomnia and DSWPD).

Choice of method: We have chosen to use the gold standard for experimental trials, RCT, as the methodological design for WP1 and 2. We want to conduct a naturalistic, yet controlled study that is generalizable to common clinical practice and outpatient psychiatric clinics. Hence, the participants will already be patients at an outpatient clinic and are not to be recruited from outside the clinic (such as from the general population). We use an RCT design to avoid confounding biases and in order to be as sure as we can that the intervention in the experimental condition represents the only difference between the groups we study. Most studies on sleep disorders exclude moderate to severe mental illness hence leaving the research results not generalizable to the patient group that may benefit from sleep interventions the most leaving a large knowledge gap regarding these patient groups. In this project, however, that is the specific

group we want to recruit and investigate, and we seek to close this gap concerning the effects of evidence-based treatment studies for sleep disorders. Since we are investigating a tormented and vulnerable group of patients that traditionally have low daytime function and tend to receive welfare, we find it particularly important to have user representatives as part of the project group to speak for the patients.

Inclusion and exclusion criteria for WP 1 and 2:

Inclusion criteria:

- Patients referred to, are offered, and who accepts attendance at the sleep-school at Bjørgvin DPS psychiatric hospital (BDPS)
- Patients fulfilling the Diagnostic Manual for Mental Disorders (DSM-V) criteria for insomnia/DSWPD
- Patients who have comorbid moderate to severe psychiatric illness operationalized as;
 1. Confirmed clinician-evaluated F-diagnosis based on the International Statistical Classification of Diseases and Related Health Problems (ICD-10/11) diagnostic system that are used in Norway
 2. *and/or* scores of >19 on BDI and/or scores of >15 on BAI at the time of referral to the sleep school

Exclusion Criteria:

- Nightwork or shift work that overlaps with the patients' regular bedtime
- Not able to fill out questionnaires online even with help from others (either because of language barriers, functionality barriers or ability level)

Power analysis for the insomnia RCT

Power analysis was conducted with G*Power, version 3.1.9.2 [15]. Relevant effect sizes (Hedges g) for power analyses were based on a recent meta-analysis of randomized controlled trials aiming at improving sleep, but that also reported an impact on mental health. The meta-analysis reported (following the removal of outliers) a large pooled effect size ($g = 0.97$) on sleep quality. The pooled effect size for composite mental health outcomes was $g = 0.42$ [16]. Another relevant meta-analysis on the effects of CBTi in patients with mental disorders and comorbid insomnia showed that effect sizes (Hedges g) for reduction of insomnia severity post-treatment were 0.50 for patients with depression, 1.50 for patients with PTSD, 1.40 for patients with alcohol dependency, 1.20 for patients with psychosis/bipolar disorder, and 0.80 for patients with mixed comorbidities, respectively. Effects on mental health symptom severity post-treatment were 0.50 for depression, 1.30 for PTSD, 0.90 for alcohol dependency (only one study), 0.30 for psychosis/bipolar, and 0.80 for mixed comorbidities [17]. Against this background an assumed effect size (Cohens d) for insomnia symptoms (primary outcome) of 0.80 was expected, whereas an expected effect size of 0.40 was deemed reasonable for the secondary (mental health) outcomes. Analyzing the data using ANOVA, setting the alpha to .05, power ($1 - \beta$) set to .80, and the correlation coefficient between repeated measures to $r = .50$, showed that 16 patients are needed to detect significant time (pre-post) x group (treatment vs. wait-list) interaction effects. In terms of the secondary outcomes ($d = 0.40$), a similar power analysis showed that a total of 52 patients are required. Taking into consideration an attrition rate of 10%, we aim, based on this power analysis, to recruit a total of 60 patients. For the sub-sample in the treatment group using additive bb-glasses, we base our power calculation on a study reporting ES of 1.6 [18]. Following the same procedure as above, we need 6 participants to show a significant time (pre-post) x group (standard care vs. treatment) interaction.

Power analysis for the DSWPD RCT

The power analysis for the delayed sleep-wake phase disorder (DSWPD) group was based on estimates of changes in dim light melatonin onset, which is one of the most important primary outcomes. Based on a previous controlled study [19] we calculated the effect size, using the Comprehensive Meta-Analysis, version 4.0, [20] in favor of the bright light intervention on this parameter to equal a Cohens d of 0.64 at posttreatment. Based on this we assumed an effect size (Cohens d) for DLMO (primary outcome) of 0.60. Setting the alpha to .05, power ($1 - \beta$) set to .80, and the correlation coefficient between repeated measures to $r = .50$, showed that 24 patients are needed to detect significant time (pre-post) x group

(treatment vs. wait-list) interaction effects. No previous study has investigated secondary (mental health) outcomes of light treatment for DSPRD. Hence, we assumed a similar effect size ($d = .40$) as for the secondary outcomes related to CBTi for insomnia. As shown above, recruiting 60 patients should then be sufficient, also when taking attrition into account. Taken together the power analyses showed that for detecting significant improvement on the primary outcome measures for insomnia and the DSWPD-group post-treatment 16, and 24 patients need to be recruited, respectively. However, in order to be able to detect improvement in the secondary outcomes and to take attrition into account as well we should recruit 60 patients in total, in each of the two patient groups. No study has investigated the additive effect of bb-glasses to light therapy at gradually advanced timing for DSWPD.

Randomization procedures: Randomization was performed by: <https://www.randomizer.org/> before inclusion. When a new patient is referred to the sleep team and meets the inclusion criteria evaluated in an individual pre-consultation before the group-based sleep-school, the patient is asked if they want to participate in the study. If they say yes, they are assigned either to Sleep-school or waitlist while in treatment as usual (TAU + WL) based on a pre-defined list. All receive a date the Sleep-school starts without being told whether or not they are assigned to a wait-list condition. They are also assigned a date for data collection at two time-points. For the Sleep-school group this is before (T1) and after (T2) Sleep-school, while for those in the TAU + WL condition are assigned T1 and T2 at least 8 (WP1) or 6 (WP2) weeks apart before they start the Sleep-school. Hence, blinding is not completely ensured, but not overt. Wait-list for specific treatments in psychiatric care is normal.

Stability in the treatment in the Sleep-school: The content (slides, hand-outs, video material) and the plan for each session in the sleep-school remains the same throughout the project. The structure has been tested over 4 years before we started recruiting and hence it is well tested. [name] and [name] has lead these groups together as co-therapists since 2017 and plan to continue until 2026 and onwards. In case of sick-leave or other unexpected circumstances, there are colleagues who can fill in for the sleep team. To ensure that the included patients receives the same treatment, we will not change the content or the structure of the sleep-school as long as we are collecting data for these projects. TAU will naturally vary with different therapists. This study is a naturalistic study in a clinic as it is, which will increase generalizability of our research.

Risks: In terms of risks and risk-mitigation table 1 below presents an overview

Table 1: Risk and risk-mitigation related to the project

Risk	Probability	Severity	Mitigating action
Problems recruiting patients	Low	High	If occurring, advertising to increase recruitment is possible and multi-sites may be established in Helse-Bergen.
Equipment malfunction	Medium	Medium	Continuously ensure data quality. Have stand-by replacement equipment
Unequal gender balance	Medium	Medium	Take this into account in the analyses and analyze for gender differences.
Adverse events	Medium	High	We can not rule out the possibility of suicide attempts or suicidal behavior occurring while participating in the study. If that happens, the clinic has procedures for such events and trained personnel available.

Ethical considerations: The two work-packages will be carried out according to the Helsinki-declaration, the Vancouver-recommendations, Good clinical practice (GCP), and CONSORT-guidelines. The project is approved by the Regional Ethics Committee of Western Norway, REK West, project number: 66304, and both WP are registered in ClinicalTrials.gov. The projects are also registered at helsenorge.no. Patients that are referred to the sleep school that decline participation in the research project or that do not meet the inclusion criteria, will still receive the treatment if considered to fulfill criteria for participating in the Sleep-

school otherwise. The wait-list group will start the active sleep school treatment immediately after the 6- or 8 weeks of waiting (waitlist guarantee), while in treatment as usual for their psychiatric illness.

Gender perspectives: We will aim at recruiting 50% men and 50% women to the studies and if we end up with unequal gender balance, we will take this into account in the analyses and analyze for gender differences.

Stakeholder considerations: Sleep problems are common, but a widespread available treatment is not common. This project may provide a feasible solution to this lack of available non-pharmacological treatment and can be implemented on all levels in the health care.

2. Impact

The results can provide valuable knowledge on the association between sleep disorders and psychiatric illness and inform on the impact of an effective and time-efficient treatment for the most common comorbidity in psychiatric care. If the results show that group-based sleep-interventions can reduce both sleep problems and psychiatric symptoms to a larger extent than treatment as usual, we will recommend a change in clinical practice. Therapists are often overloaded with patient work and may then be relieved of treating patients with comorbid sleep and psychiatric illness - and focus on patients and treatments that require individual therapy. This can lead to shorter successful treatment for those where sleep is their main problem and can lead to cost-effectiveness in the health-economy. The structure of this group-based treatment is possible to implement in district psychiatric centers (DPS) nationally and can potentially improve public access to sleep treatment, which is highly beneficial since insomnia is a predictor of subsequent work disability [21]. This can also give GPs a highly welcomed non-pharmaceutical treatment option to refer patients to instead of giving them hypnotics or antidepressants for their sleep problems [22]. The results from this project can be the beginning of the important task of closing the knowledge gap between state-of-the-art science within the sleep area and the need for improved interventions and models in psychiatric clinics.

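### The protocol lists seven (WP1) and five (WP2) primary outcomes but sizes one sleep outcome per trial as primary and mental health as secondary; no success rule is given, and the stated 80% power does not carry over to the joint primary hypothesis

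*Protocol*

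**What the plan says.** All places are in the protocol.

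- **Section 1.3, WP 1.** The list begins "Primary outcome measures: Insomnia Severity Index (ISI), the Bergen Insomnia Scale (BIS), and Sleep Onset latency (SOL), Wake after sleep onset (WASO" and ends "Sleep efficiency (SE) from sleep diaries, Becks Depression Inventory (BDI-II) and Becks Anxiety Inventory (BAI". That makes seven primary outcomes: ISI, BIS, SOL, WASO, SE, BDI-II and BAI. The primary hypothesis is that the intervention "reduces insomnia symptoms and symptoms of anxiety and depression significantly more than treatment as usual".
- **Section 1.3, WP 2.** The list is "intraindividual variation of rise time (IIV), dim light melatonin onset (DLMO), rise /wake up-time), Becks Depression Inventory (BDI-II) and Becks Anxiety Inventory (BAI": five primary outcomes, taken from diaries, actigraphy and saliva. The text does not say whether the diary or the actigraph defines rise time and its variation. The primary hypothesis again joins sleep timing to anxiety and depression.
- **Section 1.3, power analysis for the insomnia RCT.** The sizing reads "Analyzing the data using ANOVA, setting the alpha to .05", with power .80. Insomnia symptoms carry the primary label (d = 0.80, 16 patients). The mental health outcomes are labelled secondary (d = 0.40, 52 patients). With 10% attrition the target is 60.
- **Section 1.3, power analysis for the DSWPD RCT.** DLMO carries the primary label (d = 0.60, 24 patients), yet it is also described as "dim light melatonin onset, which is one of the most important primary outcomes". Mental health is again labelled secondary.
- **Section 2, Impact.** A change in clinical practice will be recommended on this condition: "If the results show that group-based sleep-interventions can reduce both sleep problems and psychiatric symptoms to a larger extent than treatment as usual".

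**The concern.** BDI-II and BAI are primary in the outcome lists and secondary in the sizing. The sizing labels do not settle which outcome decides. Insomnia symptoms could mean ISI or BIS, and DLMO is one of several primaries. No sentence says whether one outcome, some or all must be significant for the primary hypothesis to be supported.

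This matters because the two natural readings break different promises. If all parts must succeed, the error rate is controlled, but the .80 was calculated for one outcome at a time. If any one outcome suffices, .05 is no longer the trial's error rate. With the rule open, the reading can be chosen after results are known. Section 3.2 reports that effect sizes by arm for ISI, sleep efficiency, depression and anxiety were already examined in the first nine WP1 patients; no such look is reported for WP2. The recommendation in section 2 depends on how the rule is read.

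**Working it through.** **Inputs.** From section 1.3: alpha .05, power .80, correlation between repeated measures r = .50, d = 0.80 (insomnia symptoms), 0.60 (DLMO), 0.40 (mental health), 60 recruited, 10% attrition. Completers: 60 × 0.9 = 54. Assumed, because the protocol does not give them: 1:1 allocation, correlations between outcomes, d = 0.80 for all five WP1 sleep outcomes and d = 0.60 for all three WP2 sleep outcomes.

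**Reproducing the protocol's figures.** The method is the time × group interaction in a repeated-measures ANOVA with two groups and m = 2 time points: f = d/2, λ = f² × N × m/(1 − r), noncentral F with 1 and N − 2 degrees of freedom.

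| d | N | λ | Power |
|---|---|---|---|
| 0.80 | 16 | 0.16 × 16 × 4 = 10.24 | .845 |
| 0.60 | 24 | 0.09 × 24 × 4 = 8.64 | .802 |
| 0.40 | 52 | 0.04 × 52 × 4 = 8.32 | .807 |

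Each stated N is the smallest even N that reaches .80. Each is for a single outcome at an undivided .05.

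**Joint claim at 54 completers.** Power per outcome:

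- d = 0.40: λ = 0.04 × 54 × 4 = 8.64, power .822
- d = 0.60: λ = 0.09 × 54 × 4 = 19.44, power .991
- d = 0.80: λ = 0.16 × 54 × 4 = 34.56, power .9999

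If outcomes are independent, WP1 gives .9999⁵ × .822² ≈ .68 and WP2 gives .991³ × .822² ≈ .66. With a common correlation between outcomes (simulation of equicorrelated normals):

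| Correlation | 0 | .3 | .5 | .7 | .8 |
|---|---|---|---|---|---|
| WP1, all seven | .676 | .699 | .718 | .742 | .756 |
| WP2, all five | .659 | .690 | .714 | .741 | .757 |

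BDI-II and BAI account for almost all of the shortfall. Cutting the sleep part to one outcome per trial leaves joint power at about .70, .72 and .74 at correlations .3, .5 and .7 in both trials. For 80% joint power, about 64–68 completers (72–76 recruited) would be needed at correlations .5 to 0.

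**If any one outcome sufficed at .05.** With independence, 1 − .95⁷ = .302 and 1 − .95⁵ = .226. With a common correlation:

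| Correlation | 0 | .3 | .5 | .7 |
|---|---|---|---|---|
| WP1, any of seven | 30% | 27% | 23% | 18% |
| WP2, any of five | 23% | 21% | 18% | 15% |

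About half of each is a false claim in favour of treatment. In WP1 this is 14%, 11% and 9% at correlations .3, .5 and .7, against 2.5% for one test.

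**The case against.** A reader might infer that each trial carries an 18–30% false-positive risk. The protocol does not support that.

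- The range belongs to WP1; WP2 gives 15–23%.
- The upper ends need independent outcomes, which is unlikely when ISI and BIS overlap and SOL, WASO and SE come from one diary.
- Counting any single success fits the text least. The hypotheses join sleep, anxiety and depression, and section 2 asks for both sleep and psychiatric benefit.
- Testing each outcome at .05 is an inference, since alpha appears only as a sizing input. A multiplicity procedure may stand in a statistical analysis plan that is not shown, so its absence here is no finding.

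A reader might also infer that the protocol promises 80% power for the joint hypothesis and misses it. It does not: .80 is stated outcome by outcome. Nor does it follow that WP2 has seven primaries through separate diary and actigraph versions, because that sentence is ambiguous.

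These objections limit the size of the point. What stands is that the protocol itself fixes the primary outcomes in two incompatible ways. An analysis plan would still have to choose between them.

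**Conclusion.** The point holds as an inconsistency in the definition of the primary outcomes and as a missing success rule, in both trials. It should be settled before the final data are analysed. The contradiction over whether BDI-II and BAI are primary or secondary needs no calculation.

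For the joint claim that the wording suggests, power is about 68–76% in WP1 and 66–76% in WP2 at 54 completers. This rests on the assumed between-outcome correlations (0 to .8), on the effect sizes extended across the sleep measures, and on accepting the protocol's formula. If d were instead the between-group difference in change, BDI-II and BAI would each have about 30% power at 54 completers, and the shortfall would be larger. The false-positive figures are conditional: they apply only if one significant outcome at an unadjusted .05 were accepted as support.

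**What to change.** 1. Reconcile the primary and secondary labels between the outcome lists and both power analyses in section 1.3.
2. Name one primary outcome at T2 per trial: DLMO in WP2 and one insomnia-symptom scale in WP1. ISI is a reasonable choice, but the sizing text does not name it. State that the choice was made without regard to the nine-patient look, in which ISI had the largest reported effect.
3. Then test BDI-II and BAI in that fixed order, each at two-sided .05. Make the joint claim and the section 2 recommendation only if every step passes.
4. Make the other sleep measures secondary, and state whether diary or actigraphy defines rise time and its variation.
5. Restate power for the joint claim as about 70–74% (correlations .3 to .7) on the protocol's own formula. The fixed order controls error but does not bring power back to 80%.

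The cost is protocol wording and a registry update, with no extra patients or data. BIS, the diary measures, rise-time variation and rise time lose primary status, and BAI is not confirmatory if BDI-II fails.
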